**1. Abstract**

- a. Provide no more than a one page research abstract briefly stating the problem, the research hypothesis, and the importance of the research.

The incidence of shoulder replacements is quickly rising with the growing elderly population and new technologies, such as the reverse shoulder replacement. At this time, there are 53,000 shoulder replacements performed annually according to the Agency for Healthcare Research and Quality. The interscalene (IS) brachial plexus nerve block is considered the gold standard for shoulder anesthesia. While complications for IS nerve blocks are rare, they include chronic neurologic complications and substantial respiratory, cardiovascular, and central nervous system events. Femoral nerve blocks used in total knee arthroplasty are associated with complications such as insomnia, antalgic ambulation, and difficulty with rehabilitation, and increased incidence of falls.

A new approach to postoperative analgesia is the periarticular injection method, by which the surgeon administers local infiltration analgesia without the help of an anesthesiologist. Recent literature has shown that the liposomal bupivacaine (Exparel®) injection provides better pain control, shortens hospital stays, and decreases costs for total knee and hip arthroplasties compared to the gold standard nerve block methods. Broome et. al found that total knee arthroplasty patients who had a liposomal bupivacaine injection saved an average of \$600 compared to those who received a femoral nerve block. This translated to a savings of approximately one million dollars per year at their hospital alone. Eliminating the costs associated with interscalene nerve block administration in shoulder replacements could allow for significant cost-savings to our healthcare system.

Currently, no published literature exists directly comparing liposomal bupivacaine and interscalene (IS) nerve blocks in shoulder replacements. This study would provide a direct comparison of available postoperative analgesia techniques for shoulder arthroplasty. The results of this work will demonstrate whether the liposomal bupivacaine injection technique results in the same postoperative pain compared to the typical interscalene nerve block method.

**2. Objectives (include all primary and secondary objectives)**

**Aim #1:** Determine clinical outcomes as they relate to pain control of the interscalene nerve block vs. liposomal bupivacaine injection in patients undergoing total shoulder arthroplasty.

This will be evaluated using the Visual Analog Scale (VAS) pain score and pain medication data and side effects from opioids (nausea/vomiting, GI distress, itching, etc) from inpatient medical records and through daily follow-up questionnaires after patients are discharged until 96 hours after surgery. Data will be collected at routine clinical follow up appointments after surgery.

**Aim #2:** Determine the length of stay of liposomal bupivacaine compared to interscalene nerve block in patients undergoing total shoulder arthroplasty and calculate costs associated with any differentials.

**3. Background** (briefly describe pre-clinical and clinical data, current experience with procedures, drug or device, and any other relevant information to justify the research)

We conducted a retrospective cohort analysis of 58 shoulder arthroplasties performed by a single surgeon. Patients who underwent total, reverse, and hemiarthroplasties were included. The control group included patients who received interscalene nerve blocks for postoperative pain control. The experimental group included patients who received periarticular liposomal bupivacaine injections. Baseline demographic data included age, sex, body mass index (BMI), and American Society of Anesthesiologists' (ASA) classification of physical health. We measured length of stay (LOS), pain medication administration, numeric rating scale (NRS) pain scores at four time intervals postoperatively (0.5 hours, 8-14 hours, 18-24 hours, 27-36 hours). Statistical analysis was performed.

There were 21 patients in the IS nerve block group and 37 patients in the liposomal bupivacaine group who met all inclusion criteria. Baseline demographic data for age ( $p=0.53$ ), sex ( $p=0.71$ ), BMI ( $p=0.09$ ), and ASA ( $p=0.33$ ) did not differ between groups. The primary outcome measure, NRS pain score, showed no significant differences between groups at 0–1 hours after surgery ( $P = .99$ ) or 8–14 hours after surgery ( $P = .208$ ). At 18–24 hours after surgery, the liposomal bupivacaine group had a lower mean NRS score than the ISNB group ( $P = .001$ ). This was statistically significant when taking repeated measures of variance into account (Fig. 1). Mean NRS score was also lower for the liposomal bupivacaine group at 27–36 hours after surgery ( $P = .029$ ). This was not statistically significant when repeated measures of variance were considered (Table II).

There was no difference in the amount of intravenous acetaminophen given during the hospital stay between groups. There was no statistically significant difference in opioid consumption on postoperative day 1 in the hospital ( $P = .59$ ). However, there were significant differences between groups on postoperative days 2 and 3 (Fig. 2). On postoperative day 2, the ISNB group required significantly more opioids (112 mg) than the liposomal bupivacaine group (37 mg) ( $P = .001$ ). The ISNB group also required significantly more opioids (25 mg) on postoperative day 3 than the liposomal bupivacaine group (5 mg) ( $P = .002$ ).

Sixteen of 37 patients in the liposomal bupivacaine group and 2 of 21 in the ISNB group (Table III) were discharged on the day after surgery. The mean LOS was  $46 \pm 20$  hours for the liposomal bupivacaine group and  $57 \text{ hours} \pm 14$  hours for the ISNB group ( $P = .012$ ).

There were no major cardiac or respiratory events in either group. No long-term paresthesias or neuropathies were noted. There were no readmissions for either group.

Liposomal bupivacaine injections may provide better pain control 18-24 hours after surgery and shorten hospital stays after shoulder arthroplasty compared to interscalene nerve blocks as a means of postoperative pain control. Based on these results, larger analytic studies including randomized trials should be performed to explore the potential benefits of liposomal bupivacaine injections for pain control after shoulder arthroplasty.

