#### 4. After Discharge:

- Patients will record the following information after discharge up until 96 hours from their surgery:
  - VAS scores every 6 hours
  - Pain medication consumption (dosages, times)
  - Opioid-related side effects
  - Level of satisfaction with pain management
- Study staff may conduct reminder phone calls to ensure patients complete outpatient data collection. The outcome assessor will be blinded to the treatment group.
- Patients will record their VAS pain scores again at their 1st postop appointment, which typically occurs 10-18 days after surgery.

Sample Size: There will be 60 patients in each group, for a total study population of n = 120.

Study Locations: This will be a multi-center study. The sample size will enroll 120 (to account for 15% drop out rate) patients total, with approximately 30 patients enrolled at each site. The other participating sites are as follows:

[name]  
Sports Medicine and Shoulder Service  
University of Texas, Southwestern Medical Center  
[name]  
[name]

[name]  
MedStar St. Mary's Hospital  
[name]  
[name]

[name]  
William Beaumont Army Medical Center  
[name]  
[name]

**Aim #2:** Determine the length of stay of liposomal bupivacaine compared to interscalene nerve block in patients undergoing total shoulder arthroplasty and calculate costs associated with any differentials.

- b. Study duration and number of study visits required of research participants.

Patients will be enrolled in this study for 2 weeks after their surgical date. This time frame will include their hospital stay and include their time at home after discharge up until 96 hours after their surgery, and their 2-week postop appointment data. If patients are not scheduled for their postop appointment within 10-18 days after surgery (which is standard clinical practice), the study team will call the patient to obtain their pain score and medication data. Patient names will be stored in a password-protected database for 30 days after discharge to calculate 30-day readmission rates.

Routine patient follow up is typically at 3, 6, and 12 months for the first year. Pain data and patient reported outcomes are collected at these visits as routine clinical care. Patients routinely complete the ASES and EQ-5D questionnaires at their 12 month follow up appointment.

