- c. Blinding, including justification for blinding or not blinding the trial, if applicable.

Patients will be masked by performing the ISNB under sedation. They will not be completely blinded to their treatment group due to the fact that the Exparel group will not get a needle puncture at the site of the typical ISNB location in the neck since Exparel is injected intraoperatively in the surgical field while the patient is completely under general anesthesia. While the patient and surgeon cannot be blinded for this study, the outcome assessor will be masked to prevent bias in the data collection process.

- d. Justification of why participants will not receive routine care or will have current therapy stopped.

N/A

- e. Justification for inclusion of a placebo or non-treatment group.

N/A

- f. Definition of treatment failure or participant removal criteria.

Treatment is a one-time intervention for the nerve block. The assessment of their VAS pain score is routine clinical practice.

- g. Description of what happens to participants receiving therapy when study ends or if a participant's participation in the study ends prematurely.

In these cases, routine clinical care will continue based on the patient's needs.

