## 7. Study Statistics

- a. Primary outcome variable.

- VAS pain score at 24 hours postop.

- b. Secondary outcome variables.

- VAS scores at all other data points,

- Pain medication consumption (narcotics, NSAIDs, Tylenol)
- Opioid-induced side effects (nausea, vomiting, constipation)
- Length of hospital stay
- 30 day readmission rate.

- c. Statistical plan including sample size justification and interim data analysis.

A power analysis was performed to determine the sample size needed to determine noninferiority between groups with respect to VAS pain score. The minimal clinically important difference of VAS is 1.4 cm^13. The number was found to be 42 patients in each group, for a total n = 84. To ensure we reach this number, each of the 4 sites will aim to enroll 30 patients, to account for drop out.

The age of the two treatment groups will be compared using t-test. Sex distribution and the ASA scores of the groups will be compared using a chi-squared test and a Fisher exact test, respectively.

The median and interquartile range of the VAS scores at each of the time points measured will be tabulated by treatment group, and at each time point the difference between groups will be tested using non-parametric rank sum tests.

We will test the longitudinal trajectory of VAS scores over time, taking into account repeated measurements in the same patients using linear mixed model analysis. Treatment group, time period as a categorical variable, and the interaction between treatment and time period will be included as fixed effects, and patient ID will be included as the random effect. An initial omnibus test will be performed for all treatment and treatment by time interaction effects. If significant, the treatment by time interaction will be tested subsequently for each of the measurement periods.

The association of day of discharge (as a categorical variable) with treatment will be tested using the Fisher exact test.

- d. Early stopping rules.

We will monitor operative and post-operative complications including implant failures, nerve injuries, hematomas, and infections. We do not anticipate issues with these complications, as both techniques are in routine use in our current clinical practice. We did not find any differences in the complication rates in our retrospective cohort analysis.

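### Pain scores come from the chart before discharge and a patient form after it, VAS administration is not standardised, and discharge timing may differ by arm

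*Combined protocol and SAP*

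**What the plan says.** The primary outcome in section 7a is "VAS pain score at 24 hours postop"; VAS scores at all other points are secondary. Aim 1 in section 2 collects VAS scores, pain medication and opioid side effects "from inpatient medical records and through daily follow-up questionnaires after patients are discharged until 96 hours after surgery". Section 4a lists six-hourly VAS scores among the inpatient data items, and six-hourly VAS scores that patients record themselves at home up to 96 hours. Section 4f adds: "The assessment of their VAS pain score is routine clinical practice".

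The sizing statement in section 7c is in VAS units: "The minimal clinically important difference of VAS is 1.4 cm", followed by "The number was found to be 42 patients in each group, for a total n = 84". The analysis there is a rank sum test at each time point and a linear mixed model with treatment, time, their interaction and a patient random effect. Nothing in it refers to how a score was obtained.

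Section 3 describes the retrospective cohort behind the trial. It measured "numeric rating scale (NRS) pain scores at four time intervals postoperatively", and it reports that "Sixteen of 37 patients in the liposomal bupivacaine group and 2 of 21 in the ISNB group" were discharged on the day after surgery, with length of stay 46 ± 20 h and 57 ± 14 h respectively.

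**The concern.** A score that staff enter in a chart and a score that a patient marks alone on a form can differ systematically, even if both are called a VAS. The protocol does not say whether the VAS is a marked line or a spoken number, who records it in hospital, or how charted and self-recorded values are combined. The pilot's use of an NRS makes it a fair question what the charts hold, because the 1.4 cm figure applies only to scores on that scale.

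The change of mode would be harmless if it happened at the same time in both arms. It happens at discharge, however. Discharge timing is itself an outcome (Aim 2), and it differed by group in the pilot. Mode is thus a post-randomisation variable, so randomisation does not balance it. A constant shift between modes becomes an arm difference in proportion to the gap in the share already home. Since that gap varies over time, the shift can also look like a treatment-by-time interaction, which is the effect that the mixed model tests.

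**Working it through.** **The plan's own figure.** The 42 per group cannot be reproduced, because section 7c gives no SD, alpha or power. Solving SD = 1.4 × √(42/2) / (z for alpha + z for power) gives 2.29 (one-sided 0.025, 80% power), 1.98 (0.025, 90%), 2.58 (0.05, 80%) or 2.19 (0.05, 90%). The first is used below for illustration.

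**Pilot discharge (section 3).** 16/37 = 43.2% and 2/21 = 9.5%, a gap of 33.7 points (Fisher exact p = 0.009). This counts calendar-day discharges, not patients home by 24 h.

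**Share already home at hour h.** Treat pilot length of stay as normal, with the ± figures as SDs and the clock starting at about the time of surgery. The share home is Φ((h − 46)/20) for liposomal bupivacaine and Φ((h − 57)/14) for the block. At 24 h these are Φ(−1.10) = 13.6% and Φ(−2.36) = 0.9%.

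**Spurious arm difference** = gap in share home × mode shift. The shift of 0.5 to 1.0 cm is an assumption; the documents give neither a size nor a direction.

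| Hours | Liposomal bupivacaine home | Block home | Gap (points) | Spurious difference (cm) |
|---|---|---|---|---|
| 24 | 13.6% | 0.9% | 12.6 | 0.06 to 0.13 |
| 36 | 30.9% | 6.7% | 24.2 | 0.12 to 0.24 |
| 48 | 54.0% | 26.0% | 28.0 | 0.14 to 0.28 |
| 72 | 90.3% | 85.8% | 4.5 | 0.02 to 0.05 |

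At 24 h, 0.063/1.4 = 4.5% and 0.126/1.4 = 9.0%, that is, about 5 to 9% of the threshold.

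**Sensitivity.**
- If the stay is counted from admission, more patients are home at 24 h after surgery. At a stay of 27 h the shares are 17.1% and 1.6%, a gap of 15.5 points, which gives 0.08 to 0.16 cm.
- If every day-after discharge were home by 24 h, the gap would be 33.7 points, giving 0.17 to 0.34 cm (12 to 24% of 1.4 cm). This is a ceiling, not an expectation.
- For mode alone to move the arm difference by 1.4 cm, the shift would have to be 1.4/0.126, about 11 cm; at the ceiling it would be 1.4/0.337, about 4 cm.

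**Effect on power.** Use a comparison of means with SD 2.29, one-sided 0.025 and 42 per group. The standard error is 2.29 × √(2/42) = 0.50, and power is Φ((1.4 − bias)/0.50 − 1.96). With no bias this is 80%. A bias against liposomal bupivacaine of 0.063 cm gives 76%, 0.126 cm gives 72%, and the ceiling of 0.34 cm gives 56%. A bias in the other direction would favour a non-inferiority conclusion.

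**The case against.** The protocol names a VAS at every trial point, and section 4f says that VAS scoring is routine practice. The NRS appears only in the account of a retrospective single-surgeon cohort, whereas this is a prospective study at four sites. The Aim 1 wording is loose: the source phrase follows a list of several items, and section 4a lists the inpatient VAS as a data item of its own. Collection rules are identical in both arms. At 24 h nearly all patients would still be in hospital, on the pilot figures about 86% and 99%. The assumed shift has no source.

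Much of this stands, and it limits the point. A reader might infer that the instrument itself differs by arm, with an NRS in one and a VAS in the other. The documents do not support that: they specify a VAS in both settings and both arms, and mode follows discharge status, not arm. An NRS in the charts is a question to ask, not a finding.

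A reader might also add the two-week fallback, under which "the study team will call the patient to obtain their pain score and medication data", as a third mode in the same mechanism. It does not belong there. The call depends on whether a visit falls within 10 to 18 days, not on when the patient left hospital.

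The objection does not remove the change of source at discharge. Aim 1 is the only place that names an inpatient source, and it names the chart. Nor does it remove the arm difference in discharge timing seen in the pilot.

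**Conclusion.** The point holds as a modest, correctable weakness. Source and mode change at discharge, administration is not standardised, and discharge timing may differ by arm. At the primary time point the spurious difference is about 0.06 to 0.13 cm, with 0.34 cm as an extreme bound. It is larger between 36 and 48 h, up to about 0.28 cm, and small again by 72 h. It therefore matters mainly for the secondary VAS points and the treatment-by-time test. It does not by itself overturn the primary comparison.

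These sizes rest on three assumptions: pilot length of stay is roughly normal, the trial's discharge pattern resembles the pilot's, and the modes differ by 0.5 to 1.0 cm. If the modes agree, there is no bias. The plan as written would not show whether they do.

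**What to change.** In Aim 1 and section 4a:

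- Hand out at surgery the same patient-completed VAS form that is used after discharge, and use it at every six-hourly point in hospital and at home.
- Use a charted score only as a flagged backup when the form entry is missing, and confirm with each site whether its chart holds a VAS in centimetres.
- Record the mode of each score.

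In section 7c, add a sensitivity analysis restricted to form scores. This works only if the form is also used in hospital. Under the present plan, the same restriction would keep only scores from patients already home.

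The cost is protocol wording and earlier distribution of a form that the trial already needs, with no extra patients or visits. The downside is that inpatients complete a form every six hours and some entries may be missed. The charted backup covers those.

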#### **4. Study Procedures**

- a. Study design, including the sequence and timing of study procedures (distinguish research procedures from those that are part of routine care).

Study Design: After the decision to proceed with shoulder replacement surgery, patients will be asked to participate in this prospective randomized clinical trial.

Study Groups:

- Group 1 will receive interscalene nerve block.
- Group 2 will receive liposomal bupivacaine with local bupivacaine for postoperative analgesia.

Study Procedures:

1. Before Surgery: The Informed Consent process will be completed prior to any data collection. Consent will be completed after explanation of each treatment group and the data to be collected. The following baseline data will be collection prior to surgery:

- Demographics (including age, sex, BMI, work status, living environment)
- Medical and Surgical History
- ASA Physical Status Classification
- Charlson Comorbidity Index Score
- Pain History and Medications
- VAS pain score

2. Randomization: Subjects will be randomized prior to surgery into one of the two perioperative analgesia groups. Randomization will be stratified by gender.

3. Surgery/Inpatient Stay:

- Group 1: Patients in the interscalene nerve block group will be given a single shot block in the preoperative area by a fellowship-trained anesthesiologist. The shot will contain a local anesthetic like 5% Ropivacaine (5 mg/1 mL) with a 44 millimeter 22 gauge needle with the patient in the supine position.
- Group 2: The surgeon at each site will be trained prior to enrollment on the correct way to perform Exparel injections intraoperatively. The surgeon will give patients in the liposomal bupivacaine group the periarticular injection

containing 266 mg of the drug in 40 mL injectable saline in the operating room; local 0.5% bupivacaine-epinephrine will also be used not to exceed dose limits.

- Surgical/Inpatient Data Collection:
  - Pre-op procedure time
  - Surgical time
  - PACU time
  - Admission/Discharge time and date
  - Estimated blood loss
  - Procedures performed
  - Inpatient pain medications administered
  - Patient VAS scores every 6 hours after surgery

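### Aim 2 must estimate and cost a difference in length of stay, but its only planned analysis is an unadjusted Fisher test on discharge day, which gives no difference in hours and uses none of the baseline data collected

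*Combined protocol and SAP*

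**What the plan says.** **Objective.** Section 2 states Aim 2, quoted here short of its last word: "Determine the length of stay of liposomal bupivacaine compared to interscalene nerve block in patients undergoing total shoulder arthroplasty and calculate costs associated with any". Section 7b lists "Length of hospital stay" among the secondary outcomes.

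**Data collected.** Section 4a, under Before Surgery, lists "Demographics (including age, sex, BMI, work status, living environment"), "ASA Physical Status Classification" and "Charlson Comorbidity Index Score". The surgical and inpatient list in the same section includes the date and time of both admission and discharge, so stay can be computed in hours.

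**Analysis.** Section 7c gives one analysis of stay: "The association of day of discharge (as a categorical variable) with treatment will be tested using the Fisher exact test". Three of the baseline variables appear elsewhere in 7c, but only in between-group comparisons: "The age of the two treatment groups will be compared using t-test", and "Sex distribution and the ASA scores of the groups will be compared using a chi-squared test and a Fisher exact test, respectively". Work status, living environment and the Charlson index appear in no analysis. The one regression model in the plan is the mixed model for VAS, and it has no baseline covariate. Section 7c gives no method for the cost part of Aim 2.

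**Randomisation.** Section 4a stratifies by gender only. Section 7c names four sites.

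**The concern.** Aim 2 asks for a quantity: how much the stay differs and what that costs. A Fisher test on an arm-by-day table returns a p-value. It gives no difference in hours and no interval, so nothing in section 7c produces the number that the cost calculation needs, although the times to produce it are recorded.

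The test also cannot take a covariate. Age, comorbidity and home circumstances plausibly affect when a patient goes home. If they do, an unadjusted analysis leaves variation in the error term that data already in hand could remove. The trial was sized on VAS, with no precision or power target for stay, so any gain here comes without enlarging the trial. What is at stake is how wide the interval around the stay difference, and hence around the cost, will be.

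**Working it through.** **Figures to reproduce.** The plan states no sample size, power or precision for stay, so there is no planning figure to check. Section 3 reports a pilot P of .012 for stay. From the rounded summaries a pooled t-test gives P = .030 and a Welch test P = .018. The test used is not named, and nothing below depends on it.

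**Inputs**
- Pilot stay (section 3): 46 h, SD 20, n = 37 (liposomal bupivacaine); 57 h, SD 14, n = 21 (interscalene block). The difference is 11 h.
- Patients: 60 per arm (section 4a). With the 15% dropout in section 4a, 60 × 0.85 = 51 per arm. The documents do not say whether that dropout applies to stay, which is recorded in hospital, so both sizes are shown.
- Assumed: R², the share of variance in stay explained by the covariates, is 0.05 to 0.30. The documents give no figure.
- Assumed: two-sided alpha 0.05, and a true difference of 8 h as an example smaller than the pilot's.

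**Step 1. Pooled SD.** √[(36 × 20² + 20 × 14²)/56] = √(18,320/56) = 18.09 h.

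**Step 2. Unadjusted 95% half-width** = t × SD × √(2/n).
- n = 51: 1.984 × 18.09 × √(2/51) = 1.984 × 3.58 = 7.11 h.
- n = 60: 1.980 × 18.09 × √(2/60) = 1.980 × 3.30 = 6.54 h.

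**Step 3. Adjusted half-width and power.** Multiply the SD by √(1 − R²). The last two columns give two-sample t-test power for an 8 h difference.

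| R² (assumed) | √(1 − R²) | Half-width, 51 per arm | Half-width, 60 per arm | Power, 51 | Power, 60 |
|---|---|---|---|---|---|
| 0 | 1 | 7.11 h | 6.54 h | 60% | 67% |
| 0.05 | 0.975 | 6.93 h | 6.37 h | 62% | 69% |
| 0.10 | 0.949 | 6.74 h | 6.20 h | 64% | 72% |
| 0.20 | 0.894 | 6.36 h | 5.85 h | 70% | 77% |
| 0.30 | 0.837 | 5.95 h | 5.47 h | 75% | 82% |

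The equivalent gain in patients is 1/(1 − R²) − 1: 5%, 11%, 25% and 43%. For the pilot's 11 h, unadjusted power is already 86% (51 per arm) or 91% (60 per arm).

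**Step 4. The planned type of test.** The R² = 0 row is an unadjusted t-test on hours, which is not in the plan. For the Fisher test, collapse discharge day to next-day or later. With 51 per arm, exact power is 97% at the pilot rates (16/37 = 43.2% against 2/21 = 9.5%), 58% at 35% against 15%, and 36% at 30% against 15%. The last two pairs of rates are assumed. These figures are on a different scale from Step 3, so subtracting one set from the other does not measure the benefit of adjustment.

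**The case against.** The case against is substantial.

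**Not an error.** The unadjusted test keeps its error rate under randomisation, stay is secondary, and collecting baseline data creates no duty to adjust for them. This stands. A reader might infer that a chance imbalance, for instance in home circumstances, would bias the stay comparison. The documents do not support that: allocation is random, and the test's error rate already allows for chance imbalance.

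**No evidence that the covariates matter.** The pilot compared age, sex, BMI and ASA between groups but reports no association of any of them with stay. Work status, living environment and the Charlson index are not among its listed baseline data. This stands too. A reader might infer that these variables are the main determinants of discharge. That is plausible but undocumented, so the range has to include an R² as low as 0.05, where the gain is trivial.

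**Power is already high.** At the pilot rates the Fisher test has about 97% power on next-day discharge. This is correct, and it rules out reading the rise from 60% to 75% as an improvement on the planned test. The pilot was retrospective, non-randomised and from one surgeon, however, so the true effect may be smaller, and at 35% against 15% the same test has 58%.

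**What the objection leaves untouched.** High power for a test on categories still gives no difference in hours. Aim 2 needs that difference to calculate a cost, and section 7c does not supply it.

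**Conclusion.** The concern holds as a shortfall in estimation and efficiency for Aim 2. The firm part needs no assumption: section 7c contains no analysis that estimates the stay difference in hours or its uncertainty, and the stay analysis uses none of the baseline variables collected.

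The size of the precision gain is conditional. It rests on the pilot SD carrying over and on an R² that the documents do not supply. Within 0.05 to 0.30 the half-width shrinks by about 3% to 16%. Stay is likely to be skewed and clustered by day, so figures on the hour scale are approximate.

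The primary outcome is unaffected. The point does not show that the Fisher test is invalid, that its result would be biased, or that Aim 2 is underpowered at the pilot effect. It is worth acting on because the remedy is cheap and supplies what Aim 2 has to cost.

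**What to change.** In section 7c, before anyone sees outcome data by arm, name the Aim 2 analysis as follows:

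- **Outcome:** stay in hours, from the recorded admission and discharge times.
- **Model:** linear regression on treatment with robust standard errors.
- **Covariates:** sex (the stratification factor), site, age, ASA class or Charlson index (choose one in advance), and living environment as recorded, with its coding stated.
- **Report:** the adjusted difference in hours with its 95% confidence interval. Use both in the cost estimate.
- **Supportive:** the Fisher test on discharge day, as now planned.

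A proportional-odds model for discharge day is not a substitute here, because an odds ratio cannot be carried directly into a cost based on hours.

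The cost is a paragraph of SAP text and a few lines of code, with no new data. If living environment and the comorbidity measure each enter as one term, the covariates use about seven degrees of freedom (1 for sex, 3 for site, 1 each for age, comorbidity and living environment). That is small against about 102 to 120 patients. The list must be fixed in advance, since choosing covariates after seeing results would invite selective reporting.
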